5.5.3 Analysis of performance and safety endpoints

The performance and safety endpoints of the Cardioband System will be assessed by recording the echocardiographic parameters and by monitoring the patient clinical status. Safety assessments will consist of recording of all adverse events, and regular monitoring of haematology and blood chemistry parameters, and vital signs. These parameters are evaluated during the patients' follow-up visits.

Study results will be presented in tabular format. Two sided 95% exact confidence intervals will be presented where required. Continuous variables will be summarized by a mean, standard

	TRI-REPAIR – Tricuspid Regurgitation RePAIR with Cardioband Transcatheter System (TR1-1). Study protocol	
---	---	---

deviation, minimum, median and maximum. Categorical variables will be summarized by a count and percentage. If statistical tests will be done the significance level will be equal to or lower than 5%. Nominal p-values will be presented. Where confidence limits are appropriate, the confidence level will be 95%.

Baseline demographic and other baseline characteristics, together with safety analyses will be performed on all subjects.

The numbers of subjects who entered and completed each visit of the study will be provided, as well as the reasons for all discontinuations, grouped by major reason (e.g., lost to follow-up, adverse event, etc.). A list of discontinued subjects, protocol deviations, and subjects excluded from the efficacy analysis will be provided.

Descriptive statistics will be provided for the efficacy and safety outcome results.

The analysis of all adverse events will include incidence tables and incidence tables by severity, relationship to treatment and baseline parameters. Serious adverse events will be listed and discussed individually.

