3. **Risks specifically associated with the Cardioband, in addition to the general risks of annuloplasty, include, but may not be limited to the following :**Conversion to standard valve surgery; Failure to deliver the band to the intended site; tissue damage or vascular injury due to anchor insertion; Unsuccessful adjustment of the band; Tissue damage from insertion and removal of system components; Cardioband components embolism; Partial device dehiscence (anchor detachment) and disturbances to the conduction system.

The potential for the occurrence of device dehiscence, device mal-position, and residual or recurrent regurgitation requiring intervention is expected to be similar to that seen for Mitral valve repair with the Cardioband device. Clinical study for MR repair have demonstrated that Cardioband procedure is relatively safe and can reliably result in a significant reduction of the annular septo-lateral dimension and MR, and functional improvement in patients with FMR ⁴⁶⁾.

As with any device undergoing clinical investigation, there may be unforeseeable risks, which are not known at this time. Medical and/or surgical intervention may be required to correct clinical complications associated with the device procedure.

	TRI-REPAIR – Tricuspid Regurgitation RePAIR with CaRdioband Transcatheter System (TR1-1). Study protocol	[REDACTED] [REDACTED] [REDACTED]
---	---	--

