2.3 Analysis populations

Two analysis cohorts will be defined as below:

- Intent-to-treat (ITT) cohort includes all subjects who signed informed consent, met eligibility criteria, and for whom the study procedure has been attempted.
- As-treated cohort is a subject of the ITT cohort and includes all subjects for whom the study device is implanted and remains in the position at the time of the subject's exit from the procedure room.

The primary safety analysis will be performed on both cohorts with due consideration given to the required follow-up intervals for each cohort. All other analyses will be performed on the as-treated cohort.

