 - Edema
 - KCCQ
- 4.5 Adverse events
- 4.5.1 Adverse events reported by site

- 4.5.2 Serious adverse events adjudicated by CEC
- 4.5.3 Major serious adverse events after 30 day post procedure
- 4.6 Echocardiogram parameters by Core Lab
 - 4.6.1 Transthoracic echocardiogram (TTE) parameters at 30 day and 6 months
 - Tricuspid valve regurgitation degree
 - Quantitative doppler TR EROA
 - PISA EROA
 - PISA radius
 - TR vena contracta min
 - TR vena contracta max
 - TV annulus mid diastolic diameter
 - TV annulus mid diastolic diameter inflow view
 - TV annulus mid diastolic area
 - TV annulus diastolic area
 - TR regurgitant volume
 - RV TAPSE
 - LVEF
 - LVOT doppler stroke volume
 - Pulmonary artery pressure
 - Right atrial pressure
 - 4.6.2 Intra procedure transesophageal echocardiogram (TEE) parameters
 - TR severity
 - TR vena contracta min
 - TR vena contracta max
 - TV annulus mid diastolic diameter
 - TV annulus mid diastolic diameter inflow view
- 4.7 Protocol deviations

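### SAP 2.3 puts every safety table except the 30-day MSAE analysis on the as-treated cohort, so non-MSAE events in attempted but non-implanted subjects leave the incidence rates, contrary to protocol 5.5.3

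*SAP*

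**What the plan says.** SAP 2.3 defines two cohorts. The ITT cohort "includes all subjects who signed informed consent, met eligibility criteria, and for whom the study procedure has been attempted". The as-treated cohort is a subset of these subjects; it "includes all subjects for whom the study device is implanted and remains in the position at the time of the subject's exit from the procedure" (that is, on leaving the room where it was done).

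The same section then assigns the analyses: "The primary safety analysis will be performed on both cohorts with due consideration given to the required follow-up intervals for each cohort". Everything else follows one rule: "All other analyses will be performed on the as-treated cohort".

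SAP 2.1 and 3.2 confine primary safety to death, myocardial infarction, cardiac tamponade, device-related cardiac surgery and stroke, at discharge and 30 days. The remaining safety outputs are in SAP section 4: heart-failure re-hospitalization at 12 months (4.2.2), site-reported adverse events (4.5.1), "4.5.2 Serious adverse events adjudicated by CEC", and MSAEs after 30 days (4.5.3). Disposition is 4.1.2 and baseline is 4.1.3.

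The protocol's rule, in 5.5.3, is different: "Baseline demographic and other baseline characteristics, together with safety analyses will be performed on all subjects". It also calls for incidence tables covering all adverse events, and for individual listing and discussion of the serious ones.

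**The concern.** The study's objective is safety and technical success. A safety denominator that depends on leaving the room with the device in place is conditioned on procedural success. It removes the subjects in whom procedural harm may have been the reason for stopping.

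Such cases are foreseen. Among the risks specific to the device, protocol 9.3 lists "Failure to deliver the band to the intended site; tissue damage or vascular injury due to anchor insertion; Unsuccessful adjustment of the band". Among the procedural risks, it lists vessel perforation, bleeding that needs transfusion, and heart block. Unless one of these leads to an MSAE, it does not enter the ITT analysis.

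The rates affected are the ones the study is meant to supply. Both documents base the sample size on the width of the exact confidence interval for adverse event rates, and protocol 5.5.2 plans to compare complication rates with historical data.

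**Working it through.** **Step 1. Compare the two rules, output by output.**

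| Output | Protocol 5.5.3 | SAP 2.3 as written |
|---|---|---|
| MSAEs at discharge and 30 days | all subjects | ITT and as-treated |
| Site-reported AEs (4.5.1) | all subjects | as-treated only |
| CEC-adjudicated SAEs (4.5.2) | all subjects | as-treated only |
| MSAEs after 30 days (4.5.3) | all subjects | as-treated only |
| HF re-hospitalization (4.2.2) | all subjects | as-treated only |
| Baseline (4.1.3) | all subjects | as-treated only |
| Disposition (4.1.2) | numbers entering and completing each visit; population not named | as-treated only |

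The protocol does not define all subjects, but any ordinary reading includes those in whom the procedure was attempted. SAP 2.2 openly notes the protocol endpoints it drops and gives a reason. No such note accompanies the change of safety population.

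**Step 2. Identify what drops out.** The excluded group is wider than abandoned attempts: a device that was implanted but is not in position at room exit also removes the subject. For this group, the ITT analysis keeps MSAEs to 30 days and nothing else. The protocol's primary safety endpoint (5.3.1) also counts SADEs, but SAP 2.1 lists only MSAEs. A SADE that is not an MSAE therefore loses its ITT rate too.

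**Step 3. Size and direction.** There is no plan figure to reproduce: neither document gives an abort rate, and the table behind the sample size is blacked out. The counts below are assumptions. Only the 60 comes from the documents, as the maximum sample size.

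Let n be the implanted subjects, a of them with an event, and k the excluded subjects, b of them with an event.

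- As-treated rate = a/n
- All-attempted rate = (a + b)/(n + k)
- The as-treated rate is the lower of the two exactly when b/k > a/n.

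Take n = 57, a = 12, k = 3. The as-treated rate is 12/57 = 21.1% (Clopper-Pearson 95% CI 11.4 to 33.9).

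| b of 3 excluded | All attempted | 95% CI | Difference from as-treated |
|---|---|---|---|
| 0 | 12/60 = 20.0% | 10.8 to 32.3 | 1.1 points lower |
| 1 | 13/60 = 21.7% | 12.1 to 34.2 | 0.6 points higher |
| 2 | 14/60 = 23.3% | 13.4 to 36.0 | 2.3 points higher |
| 3 | 15/60 = 25.0% | 14.7 to 37.9 | 3.9 points higher |

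One event among the three is enough to make the as-treated figure the lower one, since 1/3 exceeds 12/57.

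**Step 4. Check that the remedy does not create its own bias.** The protocol synopsis follows subjects without an implant for 6 months. Protocol 6.6 follows those classed as screening failures only to hospital discharge. HF re-hospitalization (4.2.2) runs to 12 months, and late MSAEs (4.5.3) start after day 30. Adding three subjects who are no longer observed to such a denominator would turn 12/57 = 21.1% into 12/60 = 20.0% by dilution alone. These outputs need denominators matched to follow-up.

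**The case against.** **Scope of the sentence.** It sits in the SAP section on endpoints, so it could be read as meaning only the other endpoint analyses. The AE tables appear only in section 4, whose introduction is partly blacked out. Some section 4 items make little sense on an as-treated basis: whether the band was implanted would be 100% by definition. This shows that the SAP needs clarifying, and a population statement under the redaction cannot be ruled out. But the sentence is general, the readable text makes no exception, and the narrower reading is strained.

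**Serious events are not hidden.** This stands. A reader might infer that a subject with an abandoned procedure disappears from safety reporting altogether. The documents do not support that: protocol 5.5.3 still requires individual SAE listings, protocol 10.7 sends all SAEs to the CEC, and MSAEs to 30 days stay on ITT. Those MSAEs include device-related cardiac surgery, so conversion to such surgery is not lost in that period. A listing does not, however, correct an incidence table.

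**Direction.** A reader might also infer that the rates are necessarily biased downward. That does not follow. With no event among the excluded, the as-treated rate is the higher one, and the intervals in the illustration overlap heavily.

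**SADEs.** Restoring SADEs to the SAP's primary endpoint would bring device-related serious events back onto ITT to 30 days. That is true, but it would leave other AEs and SAEs, later events and baseline on the narrower cohort.

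**Status of the study.** This is an early feasibility study with no pre-specified hypotheses, and the SAP's own primary safety result is already on ITT. This bears on severity and leaves the inconsistency in place.

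**Conclusion.** The point holds in this form. SAP 2.3 contradicts protocol 5.5.3 on the population for baseline and for all safety analyses other than MSAEs to 30 days, and nothing readable declares or resolves the change. Attempted subjects without a device in position at room exit drop out of the AE, SAE and late-MSAE incidence rates, including SADEs that are not MSAEs.

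The effect on a rate runs from about 1 point of overstatement to about 4 points of understatement when 3 of 60 are excluded, under assumed counts. Understatement requires a higher event rate in the excluded subjects than in the implanted ones. That is plausible when harm causes the procedure to be stopped, but the documents do not establish it. With nobody excluded, nothing changes. The contradiction itself does not depend on the direction.

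This should be fixed, but it does not invalidate the primary MSAE analysis.

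**What to change.** Reword SAP 2.3 along these lines:

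- AE, SAE, SADE and MSAE tables, disposition and baseline characteristics are reported on all subjects in whom the procedure was attempted (ITT). As-treated versions are supplementary.
- Secondary effectiveness endpoints remain on the as-treated cohort.
- For outputs that extend beyond the follow-up of non-implanted subjects (4.2.2 at 12 months, and 4.5.3), the denominator contains only subjects under follow-up, or person-time is used. Events in non-implanted subjects are shown separately for the follow-up they have.

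The protocol synopsis (6 months for subjects without an implant) and protocol 6.6 (until discharge for screening failures) must be reconciled first, because the ITT follow-up interval depends on them.

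The cost is a change of SAP wording and of denominators in the affected tables. No new data are needed, because events are to be tabulated only over the follow-up that exists. The downside for the sponsor is that AE rates may look slightly less favourable.

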3 STATISTICAL ANALYSIS

3.1 General considerations

There are no pre-specified hypotheses for this study.

Continuous variables will be summarized with means, standard deviations, medians, ranges, and 95% confidence intervals for the mean based on a normal distribution. Categorical variables will be summarized with counts and percentages, accompanied by 95% Clopper-Pearson (i.e., exact method) confidence intervals. In addition, graphs may be created for certain endpoints as appropriate.

Nonparametric techniques may be used if the data does not meet assumptions of parametric tests.

3.2 Primary endpoint analysis

Safety

1. Major serious adverse events (MSAEs)

Death, myocardial infarction, cardiac tamponade, device related cardiac surgery, and stroke. Percentage of occurrences at discharge and 30-day post-procedure will be summarized in tables.

Technical

1. Successful Cardioband procedure
2. Cardioband completely implanted
3. Any reduction in septolateral diameter

Technical success is defined as meeting success criteria in all three categories. Percentage of success at discharge will be summarized in tables.

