5.3 Study Endpoints

5.3.1 Primary endpoints

Safety:

Overall rate of Major Serious Adverse Events (MSAEs)* and serious adverse device effects (SADE) until hospital discharge and at post-operative 30 days.

* Death, myocardial infarction, cardiac tamponade, device related cardiac surgery, stroke.

Technical Success:

Successful access, deployment and positioning of the Cardioband device and septolateral reduction at intra-procedure and discharge

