2 STUDY ENDPOINTS

2.1 Primary endpoints

Safety

Primary safety endpoints will be measured at hospital discharge and 30 days post-procedure.

1. Major serious adverse events (MSAEs)

- Death
- Myocardial infarction
- Cardiac tamponade
- Device related cardiac surgery
- Stroke

Technical success

Primary technical success endpoints will be measured throughout the procedure and at discharge.

1. Successful Cardioband procedure
2. Cardioband completely implanted
3. Any reduction in septolateral diameter

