2.2 Secondary endpoints*

Secondary endpoints will be measured at baseline, discharge, 1, 6, 12, and 24 months post procedure.

1. Tricuspid regurgitation
2. Effective regurgitant orifice area (EROA)
3. Regurgitant volume
4. Tricuspid annular plane systolic excursion (TAPSE)
5. New York Heart Association (NYHA) Class
6. Six Minute Walk Test (SMWT)
7. Kansas City Cardiomyopathy Questionnaire (KCCQ)
8. Left ventricular ejection fraction (LVEF)
9. N terminal pro B type natriuretic peptide (NT-pro BNP)
10. GOT aka aspartate aminotransferase (AST), GPT aka alanine transaminase (ALT), bilirubin
11. Blood urea nitrogen (BUN) creatinine clearance
12. Diuretic therapy

**Note. Although originally included in the protocol, secondary endpoints:*

- (a) Left ventricular end diastolic volume index (LVEDVI)*
- (b) Left ventricular end systolic volume index (LVESVI)*
- (c) Activity by wearable device*

will not be analyzed due to their limited relevance to main study objectives

Table 2. Summary of primary and secondary endpoints

Endpoint	Baseline	Discharge	1 Month	6 Months	12 Months	24 Months
MSAE		x	x			
Technical success		x				
Tricuspid regurgitation	x	x	x	x	x	x
EROA	x	x	x	x	x	x
Regurgitant volume	x	x	x	x	x	x
TAPSE	x	x	x	x	x	x
NYHA	x	x	x	x	x	x
SMWT	x	x	x	x	x	x
KCCQ	x	x	x	x	x	x
LVEF	x	x	x	x	x	x
NT-pro BNP	x	x	x	x	x	x
AST	x	x	x	x	x	x
ALT	x	x	x	x	x	x
Bilirubin	x	x	x	x	x	x
BUN	x	x	x	x	x	x
Diuretic therapy	x	x	x	x	x	x

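### The SAP drops serious adverse device effects from the protocol's primary safety endpoint without saying so

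*SAP*

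**What the plan says.** Protocol 5.3.1 defines the primary safety endpoint as "Overall rate of Major Serious Adverse Events (MSAEs)* and serious adverse device effects (SADE) until hospital discharge and at post-operative 30 days", and the synopsis repeats it. The asterisk ties the list of five event types (death, myocardial infarction, tamponade, device-related cardiac surgery, stroke) to MSAE alone, so SADE is a further component.

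SAP 2.1 says "Primary safety endpoints will be measured at hospital discharge and 30 days post-procedure" and then lists one item, MSAE, with those five types. Table 2 has an MSAE row and no SADE row. SAP 3.2 specifies the analysis as "Death, myocardial infarction, cardiac tamponade, device related cardiac surgery, and stroke. Percentage of occurrences at discharge and 30-day post-procedure will be summarized in tables". Table shell 4.2.1 has a row for any MSAE and one for each type.

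The SAP does declare some departures from the protocol. Its note in 2.2 begins "Although originally included in the protocol, secondary endpoints" and names LVEDVI, LVESVI and wearable-device activity, with a reason. It does not mention SADE.

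On populations, SAP 2.3 runs primary safety on both the ITT and as-treated cohorts and then states "All other analyses will be performed on the as-treated cohort". Protocol 5.5.3 says that baseline summaries, "together with safety analyses will be performed on all subjects".

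**The concern.** The missing component is the one that captures harm specific to the device. Protocol 9.3 lists among the Cardioband-specific risks "Cardioband components embolism; Partial device dehiscence (anchor detachment) and disturbances to the conduction system". When serious and judged to be caused by the device, each of these is a SADE, but none is one of the five MSAE types. A programmer working from the SAP would produce no SADE rate as a primary result, and a reader of the results would not learn that the primary safety endpoint is narrower than the protocol's.

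The study is descriptive: SAP 3.1 states that it has no pre-specified hypotheses. What is at stake is therefore the completeness of the main safety estimate and its interval.

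**Working it through.** **1. The two definitions side by side**

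| Place | MSAE (five types) | SADE |
|---|---|---|
| Protocol synopsis | yes | yes |
| Protocol 5.3.1 | yes | yes |
| SAP 2.1 | yes | no |
| SAP Table 2 | yes | no |
| SAP 3.2 | yes | no |
| SAP 4.2.1 | yes | no |

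The omission is the same in all four SAP places. The SAP's note on dropped endpoints does not cover it.

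**2. Whether another output fills the gap**

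SAP 4.5.2 plans a table of "Serious adverse events adjudicated by CEC". SADEs would be among those events, but the SAP states no breakdown by relation to the device, no 30-day rate and no primary status. SAP 2.3 also confines everything except primary safety to the as-treated cohort. That cohort holds only subjects who leave the procedure room with the device implanted and in position. Read literally, a SADE outside the five types in a subject without an implant enters no analysis specified in the SAP. Such subjects are foreseeable, because protocol 9.3 lists failure to deliver the band as a risk.

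**3. Size at n = 60**

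The sample size of up to 60 (protocol 5.5.1) was chosen from the width of the exact 95% interval. The table of rates and widths in protocol 5.5.2 is blacked out, so that choice cannot be reproduced; this point does not depend on it. No MSAE or SADE rate is readable, so the counts below are assumptions.

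For x subjects with an event, the Clopper-Pearson limits (the method named in SAP 3.1) are:

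- lower = 2.5% quantile of Beta(x, n − x + 1), or 0 when x = 0
- upper = 97.5% quantile of Beta(x + 1, n − x)

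The protocol does not say whether its overall rate is one pooled proportion or two separate rates, so both readings are shown. Assume 6 subjects with an MSAE, none of whom also has a SADE in the separate-rate column.

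| Subjects with a SADE only | Pooled endpoint, (6 + k)/60 | SAP reports, 6/60 | Separate SADE rate, k/60 |
|---|---|---|---|
| k = 0 | 6/60 = 10.0% (3.8 to 20.5) | 10.0% (3.8 to 20.5) | 0.0% (0.0 to 6.0) |
| k = 3 | 9/60 = 15.0% (7.1 to 26.6) | 10.0% (3.8 to 20.5) | 5.0% (1.0 to 13.9) |
| k = 6 | 12/60 = 20.0% (10.8 to 32.3) | 10.0% (3.8 to 20.5) | 10.0% (3.8 to 20.5) |
| k = 9 | 15/60 = 25.0% (14.7 to 37.9) | 10.0% (3.8 to 20.5) | 15.0% (7.1 to 26.6) |

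Each omitted SADE-only subject lowers the pooled rate by 1/60 = 1.7 percentage points. The omission can lower the pooled rate or leave it unchanged, but never raise it. If two rates were meant, the SAP's MSAE rate is right and a whole rate is missing.

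**The case against.** - **The omission may be documented elsewhere.** The SAP cites protocol Rev 05 of May 25, 2017. The revision number of the protocol reviewed here is not readable, and part of SAP section 4 is blacked out. This stands as a caveat. The protocol text available has SADE in both places, and the SAP sections that define and analyse the endpoint are readable and lack it.
- **The events would still be reported.** Protocol 5.5.3 promises incidence tables by relationship to treatment and individual discussion of each serious adverse event, and protocol 10.7 has the CEC review them all. This is true, and SADEs need not vanish from the study report. It still gives no SADE rate as a primary result.
- **The cohort conflict is a separate defect.** It affects every serious event outside the five types in subjects without an implant, whether or not the device caused it, and would remain for the others after SADE was restored. That is fair. It matters here because it shows that the other SAP outputs do not close the gap.
- **SADE needs no entry of its own.** Protocol 10.2 defines adverse device effect and serious adverse event, and the meaning follows by combining them. This is largely right, but the treatment of possibly related and procedure-only events is still open.
- **The counts are invented and no test changes.** Both are true. The illustration shows direction and scale only; the case rests on fidelity to the protocol's primary endpoint.

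**Conclusion.** The concern holds, and it must be fixed. The SAP replaces a two-component primary safety endpoint with one component and does not disclose the change, although it discloses and explains lesser changes to secondary endpoints.

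The loss is confined to SADEs outside the five MSAE types; a SADE that is also a death, infarction, tamponade, device-related operation or stroke is already counted. Under the assumed counts the pooled rate is understated by 0 to 15 percentage points at n = 60. If two rates were meant, an entire primary rate is absent. The true size is unknown because no event rates are readable. The conclusion assumes that the protocol revision cited by the SAP defines the endpoint as the available protocol does.

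**What to change.** Restore SADE to the primary safety endpoint in SAP 2.1, Table 2, 3.2 and 4.2.1. Report three rows, through discharge and through day 30, in both the ITT and as-treated cohorts, each with a Clopper-Pearson interval:

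1. subjects with at least one MSAE;
2. subjects with at least one CEC-adjudicated SADE;
3. subjects with at least one of either.

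Name the row that is primary, which settles the pooled-or-separate question, and confirm that the day-30 figure is cumulative. Define SADE as a serious adverse event that the CEC adjudicates as an adverse device effect under protocol 10.2. Before database lock, state how possibly related and procedure-only events are counted.

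If the omission was intended, say so and justify it, as the SAP does for the three dropped secondary endpoints.

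The cost is SAP wording, a counting rule agreed with the CEC, and extra table rows for two cohorts. Relation to the device is already recorded on the CRF (protocol 10.3), and the CEC already adjudicates relation to device or procedure (protocol 10.7), so no new data collection should be needed. If the CEC form does not separate device from procedure, some events would need a second look. The reported primary safety rate may be higher.
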